laryngeal mask airway can be placed for spontaneously breathing patients. Anesthesia will be maintained using the inhalational anesthetic sevoflurane (AbbVie) with an end-tidal concentration of 1.4 - 2%. The surgeon will infiltrate the arthroscopic port insertion sites with 10-40ml total volume of bupivacaine 0.25% (1:200,000 epinephrine) or lidocaine (as determined by the attending physician). Muscle relaxation will be reversed using a combination of neostigmine (0.04mg/kg) and glycopyrrolate (0.007mg/kg) if necessary. Standard anti-emetic prophylaxis with the serotonin antagonist ondansetron (4mg) will be given. For the purpose of this study, patients will not receive additional dexamethasone regardless of group allocation.

Upon arrival to the recovery room, pain (Verbal Response Score  $\geq 4$  or patient request for analgesia) will be treated with intravenous hydromorphone (solely for this study) in 0.2-0.4mg increments every 5 minutes as needed. Postoperative nausea will be treated (as needed) with an additional dose of ondansetron (1mg), droperidol (0.625mg), dimenhydrinate (50mg) or prochlorperazine at the discretion of the attending physician. Capillary blood glucose will also be assessed and recorded for this study. Once oral intake is initiated, patients will receive one of several analgesic preparations as needed: Tylenol #3® (acetaminophen 325 mg/codeine 30 mg/cafeine 15 mg per tablet), or oxycocet (acetaminophen 325 mg/oxycodone HCl 5 mg per tablet), oxycodone 5-10 mg, or hydromorphone 2-4 mg if intolerant to codeine at the discretion of the attending physician. Upon discharge from hospital, patients will receive a prescription for Tylenol #3® as needed, or hydromorphone or oxycocet if intolerant to codeine at the discretion of the attending physician.

After discharge, patients will complete a home pain diary with information that will be collected by research personnel during postoperative telephone calls. Patients will be asked to record the time at which they first experience pain at the surgical site, the time when they first consumed prescribed opioid

analgesics for surgical site pain and when they regained preoperative baseline hand strength.

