Postoperatively patients will be requested to document interval oral analgesic consumption, presence of nausea or vomiting, presence of weakness in the operative arm, and presence of paresthesia (numbness or tingling) in the operative arm. The doses of oral codeine, hydromorphone, or oxycodone consumed by each patient will be converted into equianalgesic doses (oral morphine equivalents). Conversion ratios will be employed according to the general monograph for opioids in the Canadian Pharmacists' Association Compendium of Pharmaceuticals and Specialties (36th ed., 2001) as follows: oral oxycodone: oral morphine sulphate = 1:1.5, oral hydromorphone:oral morphine sulphate = 1:5, and oral codeine: oral morphine sulphate = 6.6:1. The Opioid conversion table has been appended to this protocol.

All patients will be followed-up by telephone on post operative days 1 and 7 (+/- up to 5 days depending on patient availability) to collect the following study data: NRS pain scores, onset of pain and return of the affected hand to normal strength; side effects or complications experienced [(e.g. paresthesia - numbness or tingling, infection at ISB site) in the operative arm, and whether the numbness or tingling was located distal or proximal to the operative site]; and, the quantity, frequency and onset of opioid consumption.

Additional information will not be asked, however if an adverse event (AE) was mentioned during telephone follow-up visits, this will be documented in the AE log and assessed accordingly by the QI.

Additional follow-up telephone visits may be conducted as required in the event of a Serious Adverse Event (SAE) or Adverse Reaction (AR) and will be reported in accordance with the Site Guidance on Safety Reporting document

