**v. Secondary Outcomes**

- Time to first opioid consumption – from end of injection to time to first oral opioid consumption
- Duration of motor block - from end of injection to time of baseline preoperative biceps and hand strength
- Oxygen saturation on room air 1 hour after arrival to recovery room
- Opioid consumption on POD 1 at 12 hours/bed time if patient retires to bed before the 12hr time point), 24 hours and 7 days
- NRS for pain at 12hrs/Bed time (if patient retires to bed before the 12hr time point), 24hours, 7 days
- Blood glucose in recovery room
- Persistent paresthesia in the operative arm at 7 days
- Localized infection at block site at 7 days
- Postoperative nausea

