**viii. Trial conduct and Data collection/management**

The coordinating centre for this trial will be Sunnybrook Health Sciences Centre where the study coordinator and central data clerk will be based. A physician lead will be available at SHSC to answer patients' questions about the study as well as acting as a resource for the site specific study coordinator regarding patient eligibility and education of required hospital staff. The master randomization list will be kept at SHSC.

Data will be collected on a customized case report form (CRF) that includes all relevant demographic and intra-operative data as well as each outcome sought. Patients will be provided with a home diary to complete that will capture all outcomes sought that are not obtained in hospital. CRFs and home diaries will be completely de-identified with only patient study number, age (in years), and gender as identifiers. Data from the CRFs will be entered into a database at each site on secure, password protected computers with hospital network backup. The master file linking identifying data (name, MRN, date of birth) and study number will be kept in a separate file on a secure, password protected computer with hospital network backup.

CRFs will be divided into 2 categories: "CRFs" and "Source-CRFs". "Source-CRFs" are the documents used by the RA or patient to directly capture study data. They include: the pain diary, side effect questionnaires and the sensory and motor block assessments. "CRFs" will be completed with data transcribed from a source document. They include: Preoperative details, intra-operative data collection and medication administered in the Post Anesthesia Care Unit (PACU) and Day Surgical Unit (DSU) all obtained from medical records.

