### Data collection plan

Data will be collected according to the Source-CRFs/CRFs. All data collection will be conducted by a research staff member, either a research assistant or a co-investigator, who is blinded to the patient's treatment allocation.

1. Identifying information, exclusion criteria, surgical procedure description and anesthesia data will be collected preoperatively.
2. Procedure details, including: sedative used, procedure duration (end of injection), pain on injection and the presence of blood will be collected during the block procedure.
3. Pinprick sensation in the C4-T1 dermatomes at 10 and 20 minutes post block (to characterize presence/absence of block). Pain Sensation is characterized as a: (2) = sharp sensation, (1) = dull sensation only, or (0) = no sensation.
4. Motor function (elbow flexion for biceps) at 10 and 20 minutes post block. Power is graded using (2) = normal movement, (1) = reduced movement and (0) = no movement.
5. Intra-operative anesthesia data collection. Time of first Incision, administered anesthesia and time procedure ended.
6. Room air pulse oximetry 1 hour after admission to PACU/recovery room (to characterize respiratory function near discharge)
7. Blood Glucose level in PACU.
8. An account of analgesia administered in PACU.
9. Numerical rating scale (NRS) pain scores 1 hour after admission to PACU to PACU/recovery room
10. Information regarding post block complications (including pain and bruising around the block site) will be collected in a 1 week postoperative telephone call with the patient.
11. Time to first pain sensation in the shoulder, analgesic use and return of the affected hand to normal strength will be captured in the take home patient diary and reported at follow-up telephone calls.
12. NRS pain scores, analgesia consumption and side effects experienced will be captured at: 12hours/bed time, 24 hours and 7 days post-operatively in the patient's diary reported at follow-up telephone calls.

Upon achieving enrolment of the specified 180 patients and data is collected, the database will be verified, and analyzed by the biostatistician.

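### The ±5-day call window lets the final call fall on days 2 to 6, before the 7-day secondary and safety outcomes can be collected

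*Combined protocol and SAP*

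**What the plan says.** **Call schedule.** Section E.iii (Protocol) has all patients telephoned on "post operative days 1 and 7 (+/- up to 5 days depending on patient availability"). These calls gather pain scores, return of hand strength, complications such as paresthesia and block-site infection, and opioid use. Further calls are foreseen only after a serious adverse event or adverse reaction.

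**Outcomes.** Section E.v lists "Persistent paresthesia in the operative arm at 7 days" and "Localized infection at block site at 7 days", and also sets 7-day time points for the pain score and opioid consumption.

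**Diary.** In the Data collection plan (section E.viii), item 12 says pain scores, analgesic use and side effects are "captured at: 12hours/bed time, 24 hours and 7 days post-operatively in the patient's diary" and then reported at the calls. Section E.iii describes the same route: "patients will complete a home pain diary with information that will be collected by research personnel during postoperative telephone calls". Section E.viii gives the diary wide scope, as a "home diary to complete that will capture all outcomes sought that are not obtained in hospital".

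**Complications.** Item 10 of the Data collection plan says post-block complications "will be collected in a 1 week postoperative telephone call with the patient". No tolerance is stated there.

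**The concern.** The tolerance is two-sided and nearly as long as the interval it applies to. It therefore allows the last planned contact to happen well before the time at which four secondary outcomes are defined. The diary has a fixed 7-day entry, but an entry not yet written cannot be read out over the telephone.

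Paresthesia and block-site infection are at stake most. Perineural dexamethasone is off-label (sections C and E.ix), and section C itself raises neuropathy and neurotoxicity as the safety questions. These two outcomes are the plan's 7-day measures of nerve and block-site safety. An infection that appears after an early last call would be missed unless the patient reported it unprompted. Numbness noted on day 2 does not answer the same question as numbness that persists at day 7. For pain and opioid use, the 7-day value would be missing, or an incomplete value might stand in for it.

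**Working it through.** The plan gives no calculation on this point. Its one design calculation, the sample size in section E.vi, concerns the primary outcome and does not enter here. The check is calendar arithmetic plus a comparison of sections.

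**Inputs.** Call days 1 and 7 and a tolerance of 5 days (E.iii); outcome time of 7 days (E.v); diary entries at "12hours/bed time, 24 hours and 7 days post-operatively" (Data collection plan, item 12); expected block duration of 18 hours with perineural dexamethasone (E.vi).

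**Step 1: the permitted window.**
- Day-7 call: 7 − 5 = day 2; 7 + 5 = day 12.
- Day-1 call, if the tolerance covers it: 1 − 5 = day −4; 1 + 5 = day 6. The negative part is impossible, so the wording leaves it unclear which call is governed.

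**Step 2: what exists at the time of the call.**
- Call on days 7 to 12: the 7-day diary entry can already exist and is simply reported late.
- Call on days 2 to 6: the entry does not yet exist, and 7-day paresthesia and infection status cannot be observed.

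**Step 3: share of the 7-day opioid period elapsed at an early call** (call day ÷ 7).
- Day 2: 2/7 = 29%
- Day 3: 3/7 = 43%
- Day 4: 4/7 = 57%
- Day 5: 5/7 = 71%
- Day 6: 6/7 = 86%

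**Step 4: paresthesia.** Take day 2 as 48 hours and day 7 as 168 hours after the block, and assume the expected 18-hour duration. Time since expected block end is then 48 − 18 = 30 hours at day 2, against 168 − 18 = 150 hours at day 7.

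**Step 5: is there a second route to the data?** Sections E.iii and E.viii were compared for a later routine contact, a diary return step, or a rule for answers obtained off the nominal day. None is described. Section E.vii analyses opioid use and pain scores by repeated measures ANOVA, and paresthesia and infection by chi-square or Fisher's exact test, without saying how off-day values are handled.

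**Step 6: which item is most exposed.** Section E.iii asks patients to document analgesic use, nausea or vomiting, weakness and paresthesia. Infection is named only for the calls. The general statement of diary scope in E.viii would cover it, but no specific diary item is described.

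**The case against.** The case for the plan as written has real force, and it rules out several stronger readings.

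- **A reader might infer that none of the 7-day results are 7-day outcomes.** The documents do not support this. Item 12 fixes a 7-day diary entry, E.viii extends the diary to everything not obtained in hospital, and item 10 speaks of a one-week call. A call on day 7 or later can yield true 7-day data.
- **A reader might infer a six-fold range in opioid accumulation (12/2).** That assumes use is totalled to the date of the call. The outcome is consumption at 7 days, so a day-12 call need add nothing. Within the outcome period the extreme is 2 of 7 days.
- **A reader might infer that patients called early are counted as event-free, or as having persistent numbness.** The plan never says that an early answer is entered as the 7-day value. Missing data are equally possible. What can be said is that the handling is unspecified.
- **A reader might infer bias between arms.** The window is the same for both, and patients and assessors are blinded, so no directional effect is expected.
- **A reader might infer that the two call windows overlap.** That depends on the tolerance covering day 1, which the text leaves unclear. Overlap alone would not corrupt entries tied to fixed times.

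It can also be said that E.viii treats the diary as a source document, which might imply that it is returned. No return step is stated, and the route that is described is the telephone.

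The core point survives all of this: a stated rule permits the last routine call before day 7, and nothing in the plan requires a contact or diary retrieval on or after day 7.

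**Conclusion.** The point holds for final calls made on days 2 to 6, and only for those. For such patients the 7-day pain score, opioid use and side-effect entries cannot be collected, and 7-day paresthesia and infection status cannot be observed. At the extreme, 29% of the opioid period has elapsed.

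The total effect cannot be computed, because the documents do not say how many calls would be early. The expected harm is noise, missing data and under-ascertainment of late events in secondary and safety outcomes. No effect on the primary outcome or the sample size is identified.

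The conclusion rests on reading the tolerance literally for the day-7 call, and on the telephone being the only route by which diary data reach the study. If completed diaries are in fact returned, the diary items are largely protected. Infection would then depend on whether the diary asks about it.

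**What to change.** Amend the follow-up paragraph in section E.iii, and the Data collection plan to match:

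1. State which call the tolerance governs.
2. Require the final call on day 7 or later (0 to +5 days), and record at that call the values the diary shows for day 7.
3. Record the actual assessment day for every follow-up item.
4. If a patient is reached before day 7, call again or retrieve the completed diary. Do not analyse the early answer as a 7-day value, but keep it, with its date, as safety information. Treat the 7-day item as missing only if neither route succeeds.

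Section E.vii needs a matching sentence on the handling of off-day values.

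The cost is a few sentences and a changed call schedule. The upper limit of day 12 is kept, so most of the flexibility for patient availability remains. The downside is that patients reachable only early will need a second call or will have 7-day items missing.

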**C. Background and Rationale**

Interscalene brachial plexus block (ISB) is regarded as the standard of care for analgesia after shoulder surgery providing superior analgesia and reducing opioid consumption. ISB can have complications including ipsilateral phrenic nerve block resulting in diaphragmatic paralysis for the duration of the block which can result in temporary ventilatory compromise for patients with reduced respiratory reserve. Nonetheless, the benefits more often outweigh the risks in the appropriate patient population by reducing ventilatory depression associated with significant opioid use after painful upper extremity surgery. Shoulder surgery, previously requiring inpatient admission for pain control, is now commonly performed on an ambulatory basis facilitated by ISB analgesia. The effects of single injection ISB dissipate after several hours unmasking the moderate to severe pain of the surgical insult and require strong opioid analgesia. Efforts to prolong ISB duration by increasing local anesthetic (LA) dose are limited by their pharmacodynamics and narrow therapeutic window.

A broad cross section of surgical patients consistently ranks postoperative pain as their highest concern highlighting the necessity for prolonged and effective postoperative analgesia. Strategies to prolong ISB analgesia include the placement of indwelling perineural catheters to allow for prolonged infusion.

Indwelling catheter techniques can be very effective and provide analgesia for several days but their utility is limited by technical challenges with placement, inherent secondary failure rate, and material cost.

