#### **ix. Data safety monitoring plan**

This study involves the off-label use of dexamethasone. Consequently, an application to Health Canada will be made to obtain regulatory approval for the use of perineural dexamethasone. All adverse events will be documented (serious or not, related or not, expected or not) and reported following the Site

Guidance on Safety Reporting document. Serious adverse events are not expected. The severity of the adverse event will be coded as mild, moderate, or severe. The association with the intervention will be coded as unrelated, unlikely related, possibly related, probably related, or definitely related. The principal investigator will review all adverse events and act as safety monitor. These will be communicated to Health Canada and the Research Ethics Board of each respective institution. The independent reviewers will determine if the off-label use of dexamethasone contributed in any way to the adverse event and will make recommendations to either terminate, or modify study protocols.

The following are potential side effects often associated with surgical procedures that are not considered adverse events related to this study (obtained confirmation from five other physicians who declare no conflict of interest) and will therefore not need to be assessed and recorded by the QI in cases where these side effects are reported by study patients while they are in hospital and at home during post-operative follow-up telephone interviews:

- Headache/dizziness/nausea/vomiting/wheezing
- Bruising in the arm
- Gritty feeling in the eye/blurred vision/mild visual disturbance
- Bradycardia/tachycardia
- Complications associated with general anesthesia such as major cardiac events
- Local anesthetic toxicity
- Hemidiaphragmatic paresis (temporary)
- Hoarse voice (temporary)
- Horner's syndrome (temporary)
- Pruritus
- Changes in blood pressure
- Oxygen saturation below 90%
- Pain, cellulitis, or muscle spasm in areas other than the nerve block injection

A single interim analysis will be performed at 50% enrolment. If the data analysis indicates equipoise no longer exists, the study will be stopped early. The Haybittle-Peto threshold will be utilized (p=0.001).

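### The follow-up calls bar questions beyond a set list and the safety section exempts listed events from recording, although the plan promises to document every adverse event

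*Combined protocol and SAP*

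**What the plan says.** Section E.iii (Protocol) schedules telephone calls on postoperative days 1 and 7, with a tolerance of up to 5 days. The calls collect "NRS pain scores, onset of pain and return of the affected hand to normal strength; side effects or complications experienced", the last of these illustrated by "e.g. paresthesia - numbness or tingling, infection at ISB site) in the operative arm", and opioid use. The next paragraph reads: "Additional information will not be asked, however if an adverse event (AE) was mentioned during telephone follow-up visits"; any event so raised goes into a log for the QI to assess. Extra calls are allowed when a serious adverse event or adverse reaction has occurred.

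The home diary in the same section asks for analgesic use and for "presence of nausea or vomiting, presence of weakness in the operative arm, and presence of paresthesia (numbness or tingling) in the operative arm".

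Section E.viii adds three things. Item 10 of the Data collection plan collects block complications, including local pain and bruising, at the one-week call. Item 12 captures side effects at 12 hours or bedtime, 24 hours and 7 days, with no restriction to the arm. Side effect questionnaires are named among the source forms, but their content is not shown.

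Section E.ix states: "All adverse events will be documented (serious or not, related or not, expected or not"). It then gives a list of 13 entries regarded as not related to the study. The QI need not assess or record these when patients report them, in hospital or by telephone from home.

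**The concern.** The safety section makes an unconditional promise, and two other rules work against it. The first limits what a caller may ask, so anything outside the prompts depends on the patient raising it. The second lets a reported event go unrecorded if it is on a list. An event can therefore be lost because nobody asked, or because it was reported and then set aside.

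This matters because perineural dexamethasone is used off-label here. Under section E.ix the adverse events go to Health Canada and the ethics boards, and reviewers may recommend stopping the trial or changing its protocol on the strength of them. If few events are recorded, a reader cannot tell whether few occurred or few were sought and kept.

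Respiratory events show the gap most clearly. The Background says interscalene block can cause "ipsilateral phrenic nerve block resulting in diaphragmatic paralysis for the duration of the block", and section E.vi expects blocks of 12 to 18 hours. The one respiratory measurement is "Room air pulse oximetry 1 hour after admission to PACU/recovery room (to characterize respiratory function near discharge"). The text shows no respiratory question after discharge, and several respiratory events are on the exempt list.

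**Working it through.** No sample size, power or event figure bears on this point, so the check sets the sections side by side.

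**Step 1. What is prompted after discharge, and what may go unrecorded as an adverse event.**

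| Event after discharge | Prompt shown in the text | On the E.ix exempt list |
|---|---|---|
| Nausea or vomiting | Yes: diary (E.iii); nausea is also a secondary outcome (E.v) | Yes, but still captured through the diary |
| Arm weakness, paresthesia | Yes: diary; paresthesia also at the calls and in E.v | No |
| Infection at the block site | Yes: calls (E.iii) and E.v | No; cellulitis is exempt only away from the injection |
| Local pain or bruising from the block | Yes: E.viii item 10 | Arm bruising yes; pain only away from the injection |
| Wheezing, temporary hemidiaphragmatic paresis, saturation below 90% | None shown | Yes |
| Major cardiac event as an anesthetic complication | None shown | Yes |
| Emergency visit, readmission, other unplanned care | None shown | No, but logged only if mentioned |

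The first four rows are collected whatever the other rules say. The gap is in the last three.

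**Step 2. Section E.iii against section E.ix.** Documenting all adverse events needs some way of finding those that are not on a checklist. After discharge, the calls and the diary are the only routine contact described. A caller who follows E.iii may not ask an open question. The extra calls do not fill the gap, because they are made once the site already knows of a serious event or reaction.

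**Step 3. Section E.ix against itself.** The opening commitment applies whether or not an event is related or expected. The list later in the same section removes events because they are considered unrelated to the study. The two statements use relatedness in opposite ways and cannot both govern what is recorded.

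**Step 4. Section E.iii against section E.viii.** Item 12 captures side effects with no limit to the arm. E.iii ties its side-effect entry to the operative arm and then rules out further questions. A caller cannot tell from these two texts whether a general side-effect question is allowed.

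**Step 5. Effect on the comparison.** Section E.iii and the Data collection plan both keep the staff who collect outcomes blinded. The same calls and diary serve both arms, and both are assigned dexamethasone 4 mg. Passive collection should therefore lower the count in both arms, with no evident reason for it to favor one.

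**The case against.** The case on the other side has several sound parts.

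- *Harms are solicited.* A reader might infer that every harm the protocol names is recorded only if volunteered. The table shows otherwise: the harms set as secondary outcomes, and the common block complications, are actively sought. This part of the objection stands.
- *Unseen forms may ask more.* The side effect questionnaires and the site guidance on safety reporting are not in the text, and the call entry on side effects is given by example. It therefore cannot be shown that no form asks about breathlessness or unplanned care. That limits the claim to harms outside the prompts. It does not remove the conflict: a questionnaire that went further would contradict the bar in E.iii.
- *Dexamethasone risks left unmonitored.* A reader might infer this from the contraindications in section E.ii, such as peptic ulcer disease and systemic infection. They appear there only as reasons for exclusion, not as harms expected in enrolled patients, so they do not support the point.
- *Respiratory risk.* A reader might assume that phrenic paralysis is present throughout every block. The Background says it can occur and puts near-certainty at 10 ml or more, whereas 6 ml is injected here. The timing of the oximetry reading shows where information is thin. It does not measure what the telephone rule costs.
- *A matter of method.* Spontaneous reporting is a recognized way to collect adverse events, and E.iii does require mentioned events to be logged. That would be a sufficient answer had E.ix not promised more.

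**Conclusion.** The concern holds in a limited form. Harms outside the diary, call and questionnaire prompts reach the adverse event log only if the patient mentions them. Those on the E.ix list need not be recorded by the QI even then. Both rules conflict with the commitment to document all adverse events, and the exempt list is the sharper conflict.

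The consequence is mainly under-counting in both arms. A reader might infer bias between arms or damage to the primary equivalence result. Blinded callers and identical questions give no evident reason for the first, and the primary outcome does not depend on adverse event capture.

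The size cannot be stated as a number of events. The documents give neither a rate of post-discharge events nor the share that patients would volunteer, so any count would come from assumed rates alone. What can be stated is the scope: both calls, in all 180 planned patients, and 13 list entries.

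The conclusion assumes that callers follow E.iii as written, and that the questionnaires not shown do not already contain an open question on other health problems or unplanned care.

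**What to change.** 1. In section E.iii, delete the clause that bars further questions. Keep the requirement to log and assess any event mentioned.
2. Add one scripted open question to both existing calls, asked by the blinded research assistant: *Since discharge, or since the last call, have you had any other health problem, or any unplanned visit to a doctor, emergency department or hospital?*
3. Add to the day 1 call only: *Have you been short of breath at any time since leaving hospital?*
4. Give both answers a line on the case report form and tabulate them by arm.
5. Reconcile sections E.iii, E.viii (items 10 and 12) and E.ix. In particular, revise the E.ix list so that a reported event is recorded even when judged expected or unrelated, with that judgment entered in the relatedness coding E.ix already provides. Without this step, answers to the new questions could still be set aside under the list.

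The cost is a little more time on calls already being made, two form lines, and more minor unrelated events to log. Randomization, blinding and the primary analysis are unchanged.
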